8.4 Detection of Bias

Lack of protocol compliance and the potential for biased statistical analyses will be examined by assessing the incidence of important protocol deviations in each cohort. The clinical study team will identify and document the criteria for important protocol deviations.

8.5 Outliers

Outlier data will not be excluded unless scientifically justified.

Pharmacokinetic (PK) serum concentration data will be evaluated for outliers by visual inspection, and decisions to re-assay individual samples will be made in accordance with standard pharmacokinetic evaluation practice.

8.6 Distributional Characteristics

Where appropriate, the assumptions underlying the proposed statistical methodologies will be assessed. If required data transformations or alternative non-parametric methods of analyses will be utilized.

8.7 Validation of Statistical Analyses

Programs will be developed and maintained, and output will be verified in accordance with current risk-based quality control procedures.

Tables, figures, and listings will be produced with validated standard macro programs where standard macros can produce the specified outputs.

The production environment for statistical analyses consists of Amgen-supported versions of statistical analysis software; for example, the SAS System version 9.4 or later, **East 6.4 or later**.

9. Statistical Methods of Analysis

9.1 General Considerations

Descriptive statistics will be provided for selected demographic, safety, PK, PD and biomarker data. Unless otherwise stated, the data analysis will be conducted using subjects in the Safety analysis set. Descriptive statistics on continuous data will include means, medians, standard deviations, and ranges, while categorical data will be summarized using frequency counts and percentages. Graphical summaries of the data may also be presented. When data are summarized by time, the values recorded

against the scheduled time points listed in the protocol will be used. When assessing minimum/maximum increases or decreases over the study, all assessments, including unscheduled assessments will be used. Data listings will include all available data from all enrolled subjects unless specified otherwise.

Data analysis will occur at the following time points:

- Dose decision analyses will occur in the dose exploration cohorts and **also after enrolling 5 subjects from Cohort A and Cohort B (combined) in dose expansion cohort.**
- The primary analysis will occur when target enrollment is complete and each subject either completes 6 months on study or withdraws from the study.
- A final analysis is planned after all dose-escalation cohorts and dose-expansion subjects have ended the study.

9.2 Subject Accountability

The number and percent of subjects who were enrolled, received investigational product, completed investigational product, discontinued from investigational product (including reasons for discontinuing, completed study, discontinued the study (including reasons for discontinuing)) will be summarized by cohort.

Key study dates for the first subject enrolled, last subject enrolled, and last subject's end of study will be presented.

A subject listing and summary noting inclusion in each analysis subset will be provided for all subjects enrolled. A subject listing noting duration of AMG 224 administration, reason for discontinuation of treatment, and reason for discontinuing the study will be provided. A list of subjects screened but not enrolled (screen failures) will be provided.

9.3 Important Protocol Deviations

Important Protocol Deviations (IPDs) categories are defined by the study team before the first patient visit and updated during the IPD reviews throughout the study prior to database lock. If a snapshot is being taken during the study rather than a database lock at the end of the study, categories should be updated during the IPD reviews throughout the study prior to database lock. These definitions of IPD categories, sub-category codes and descriptions will be used during the course of the study. The final IPD list is used to produce the Summary of IPDs table and the List of Subjects with IPDs. In addition, a separate listing of all inclusion and exclusion deviations will be provided.

9.4 Demographic and Baseline Characteristics

The following descriptive summaries of the demographic and baseline characteristics will be produced: Demographic (ie, age, age groups [< 65 , ≥ 65 and ≥ 75], sex, race, ethnicity), prior line of therapies (median, range) and baseline characteristics (height, weight, Eastern Cooperative Oncology Group (ECOG) Performance Status, ECHO or MUGA, refractory status, neurological evaluation status and % of subjects exposed to duratumumab) will be summarized using descriptive statistics. If multiple races have been reported for a subject, the subject will be categorized as multiple.

A listing of the demographic and baseline characteristics will be provided. In addition listings of medical history, hepatic history, prior anti-cancer therapy and prior radiotherapy usage will be provided.

9.5 Efficacy Analyses

9.5.1 Analyses of Primary Efficacy Endpoint(s)

No efficacy parameter is considered in primary endpoints.

9.5.2 Analyses of Secondary Efficacy Endpoint(s)

Listings will be produced for all subjects in the dose-exploration cohorts and the dose-expansion cohorts indicating the time to progression, time to response, and duration of response. The proportion of subjects with a partial response to treatment or better per the International Myeloma Working Group criteria (IMWG) with corresponding exact 80% CI will be calculated using the Clopper-Pearson method ([Clopper and Pearson, 1934](#)) and tabulated for subjects treated at the MTD. The proportion of subjects with minimal residual disease and the proportion of subjects progression-free at 6 months with corresponding exact 80% CI will be calculated using the Clopper-Pearson method. Kaplan Meier curve will be presented for time to progression and duration of response with estimates for rates and 80% CI at selected weeks.

9.5.2.1 Best Overall Response Rate

The number and percent of subjects with objective response as determined by the IMWG-URC will be calculated using the Clopper-Pearson method and it will be tabulated for subjects treated at the MTD. If the preliminary MTD and the final MTD are different then a preliminary BOR, final BOR and combined BOR rate will be presented.

BOR will be calculated for subjects with prior CD38 treatment in expansion phase.

BOR will also be calculated per refractory status.

The number and percentage of subjects with a best overall response of stringent complete response, complete response, very good partial response, partial response, minor response, stable disease and progressive disease will be presented by dose.

9.5.2.2 Minimal Residual Disease Conversion Rate

The proportion of subjects with negative minimal residual disease with corresponding exact 80% CI will be calculated using the Clopper-Pearson method.

Rate of conversion of MRD negativity will be calculated as,

= (No of subjects with MRD negativity / Total person months of subjects in safety analysis set) * 100.

It would be calculated only if no. of subjects with MRD negativity ≥ 1 .

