7.5 Bone Marrow

During screening, bone marrow sample is required for all subjects. Samples will be sent to the central laboratory along with the corresponding pathology report. The tumor block is to be carefully selected by a pathologist or a skilled experienced histology associate to include generous tumor tissue using the Pathology Report as a guide. In lieu of a block, 20 unstained sections on charged slides from the same block can be submitted within 4 weeks of study day 1 to allow time to evaluate the samples, and to ask for additional samples if the initial samples are not appropriate. Analyses of tumor specific mutations or epigenetic changes may be performed (eg, somatic mutations) when the samples of tumor tissues become available. Minimal residual disease will be evaluated on the bone marrow specimen of the patients that achieve complete remission per IMWG.

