10.4.4 Secondary Endpoint(s)

10.4.4.1 Efficacy Endpoint Analyses

Listings will be produced for all subjects in the dose-exploration cohorts and the dose-expansion cohorts indicating the time to progression, time to response, and duration of response. The proportion of subjects with a partial response to treatment or better per the IMWG with corresponding exact 80% CI will be calculated using the Clopper-Pearson method (Clopper and Pearson, 1934) and tabulated for subjects treated at the MTD. The proportion of subjects with minimal residual disease and the proportion of subjects' progression-free at 6 months with corresponding exact 80% CI will be calculated using the Clopper-Pearson method. Kaplan Meier curve will be presented for time to progression and duration of response with estimates for rates and 80% CI at selected weeks.

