2.1 Objectives and Endpoints

Objectives	Endpoints
Primary	

 Evaluate the safety and tolerability of AMG 224 monotherapy in subjects with relapsed or refractory multiple myeloma 	
 Safety: Incidence of DLTs, treatment-related, treatment-emergent adverse events and clinically significant changes in vital signs, physical examinations, ECGs and clinical laboratory tests

 Determine the maximum tolerated dose (MTD) and/or recommended phase 2 dose (RP2D) of AMG 224, if possible 	
Secondary	

 Characterize the pharmacokinetics (PK) of AMG 224 when administered intravenously (IV) once every 3 weeks (Q3W) 	
 PK profile: PK parameters for AMG 224 conjugated antibody (anti-BCMA antibody with at least one DM1 molecule conjugated to the antibody), total anti-BCMA antibody (sum of unconjugated anti-BCMA antibody and AMG 224 conjugated antibody), and DM1 (total unconjugated DM1) including, but not limited to maximum observed concentration (C_{max}), minimum observed concentration (C_{min}), area under the concentration-time curve (AUC), clearance (CL), and if feasible half-life ($t_{1/2}$)

 Evaluate preliminary efficacy of AMG 224 when given as monotherapy in relapsed and refractory multiple myeloma according to International Myeloma Working Group (IMWG) uniform response criteria (Durie, 2006 and Rajkumar 2011). 	
 Overall response according to International Myeloma Working Group (IMWG) uniform response criteria, relative reduction in M-component, time to progression (TTP), duration of response (DOR)

Objectives	Endpoints
Secondary(Continued)	

 Evaluate the preliminary rate of conversion to minimal residual disease (MRD) negativity 	
 Conversion to MRD negativity

 Evaluate the incidence of anti-AMG 224 antibody formation. 	
 Incidence of anti-AMG 224 antibody formation

Exploratory	

 Correlate clinical response with B-cell maturation antigen (BCMA) expression in pre-dose bone marrow biopsies /and or bone-marrow aspirates. 	
 Quantification of BCMA expression in pre-dose bone marrow biopsy and bone-marrow aspirates

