The dose exploration part of study is aimed at determining preliminary maximum tolerated dose (MTD). The preliminary MTD is defined as the maximum dose at which fewer than one third (< 33%) of subjects enrolled in a cohort dose level experience a DLT. A final estimate of the MTD will be made based on a toxicity probability interval (TPI) Bayesian model utilizing all DLT-evaluable subjects from the dose exploration and dose expansion cohorts. Based on the TPI model, the MTD is defined as the dose with the highest probability of a DLT rate between (0.20 and 0.35) while controlling the probability of excessive and unacceptable toxicity.

Minimal Residual Disease (MRD) Negativity

Tumor load of 10^{-5} target cutoff level is considered for the definition of MRD negativity ie, less than 1 clonal cell in 10^5 normal cells is defined as MRD negative.

(Paiva B, 2015)

Objective Response

Objective response is defined as a tumor response assessment of either stringent complete response, complete response, very good partial response or partial response per the International Myeloma Working Group Uniform Response Criteria for Multiple Myeloma (IMWG-URC) and will be determined only for subjects with measurable disease at baseline as per IMWG-URC for Multiple Myeloma.

Objective response will be determined based on the responses collected using Best Overall Response/Progression CRF.

Objective Response Rate (ORR)

Incidence of either PR or better (sCR, CR, VGPR) while on study as defined by the IMWG-URC. All subjects that do not meet the criteria for objective response by the analysis cutoff date will be considered non-responders.

Percent Change From Baseline

Percent change from Baseline is the arithmetic difference between post-Baseline and Baseline divided by Baseline values times 100.

Study Day

Post study day: study day= (date - date of Study Day 1) + 1

Pre study day: study day= (date – date of Study Day 1)

Study Day 1

Study day 1 is defined as the first day of administration of the investigational product after enrollment. The day prior to Study Day 1 is considered Day -1.

Serious TEAE

Serious adverse events (SAEs) are events categorized as AEs that are starting on or after first dose of investigational product as determined by the flag indicating if the adverse event started prior to the first dose on the Events CRF and up to and including 37 days after the end of investigational product.

Time to Response (TTR)

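### Of the two planned MRD measures, the person-month conversion rate has no stop at conversion and is dropped at zero; two summary sentences also name the complement of the endpoint

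*SAP*

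**What the plan says.** The secondary objective in SAP 2.1 is: "Evaluate the preliminary rate of conversion to minimal residual disease (MRD) negativity". The matching endpoint is conversion to MRD negativity, also listed in Protocol 10.1.1. The definitions in SAP section 5 give the threshold: "less than 1 clonal cell in 10^5 normal cells is defined as MRD negative".

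SAP 9.5.2.2 then sets out two measures:

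- **A proportion.** "The proportion of subjects with negative minimal residual disease with corresponding exact 80% CI will be calculated using the Clopper-Pearson method".
- **A rate.** MRD-negative subjects divided by "Total person months of subjects in safety analysis set", times 100. The next sentence adds: "It would be calculated only if no. of subjects with MRD negativity ≥ 1".

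The summary paragraph in Protocol 10.4.4.1 points the other way. It asks for "The proportion of subjects with minimal residual disease", and SAP 9.5.2 repeats the wording.

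Testing is restricted. Protocol 7.5 states: "Minimal residual disease will be evaluated on the bone marrow specimen of the patients that achieve complete remission per IMWG".

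**The concern.** A rate of conversion should count only time in which a subject could still convert. The SAP neither defines person-months nor ends them at conversion. On a literal reading, months after conversion go into the denominator.

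Follow-up is likely to be unequal. Protocol 3.1 lets dosing continue until progression, intolerance or withdrawal, and Protocol 3.5.2 lets subjects still active at the primary analysis stay on. Only complete responders are tested, so converters will tend to be among the longest-followed subjects. The more durable their responses, the lower the stated rate.

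This matters because the objective speaks of a rate of conversion, and the person-month figure is the one that SAP 9.5.2.2 labels in those terms. A reader may take it as the answer to the objective. It has no stated confidence interval, and it vanishes when the count is zero. A programmer working from the summary paragraphs alone could also produce the complement of the endpoint.

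**Working it through.** **The plan's own figure.** No figure is stated for MRD. The only one that uses the same interval method is the response-rate example in Protocol 10.2 and SAP 3.2: 20 subjects, 20% response, 80% interval 9% to 36%. Clopper-Pearson for 4/20 at two-sided 80% gives 9.02% to 36.07%, and the F-quantile code in SAP Appendix A gives the same. The figure reproduces.

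**Inputs for the rate.** From the documents: about 60 subjects in total, up to 20 of them in expansion (SAP 3.2). Assumed, because the documents are silent: number of converters x, month of conversion c, follow-up of converters Fc and of the others Fn. The Safety Analysis Set spans both parts, so N = 60 is the closer case; N = 20 applies if the expansion part is tabulated alone.

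- Total person-months: T = (N − x)·Fn + x·Fc
- Person-months at risk: R = (N − x)·Fn + x·c
- Rate as written: 100·x/T. Rate on time at risk: 100·x/R.
- Shortfall of the written rate: 1 − R/T = x·(Fc − c)/T

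**Equal follow-up (Fc = Fn = F).**

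| N | x | F | c | T | R | As written | At risk | Shortfall |
|---|---|---|---|---|---|---|---|---|
| 60 | 1 | 6 | 3 | 360 | 357 | 0.278 | 0.280 | 0.8% |
| 60 | 4 | 6 | 3 | 360 | 348 | 1.11 | 1.15 | 3.3% |
| 60 | 4 | 12 | 2 | 720 | 680 | 0.556 | 0.588 | 5.6% |
| 20 | 4 | 6 | 3 | 120 | 108 | 3.33 | 3.70 | 10.0% |
| 20 | 4 | 12 | 2 | 240 | 200 | 1.67 | 2.00 | 16.7% |

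**Converters followed longer (Fn = 3, Fc = 12, c = 3).**

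| N | x | T | R | As written | At risk | Shortfall |
|---|---|---|---|---|---|---|
| 60 | 2 | 198 | 180 | 1.01 | 1.11 | 9.1% |
| 60 | 4 | 216 | 180 | 1.85 | 2.22 | 16.7% |
| 20 | 2 | 78 | 60 | 2.56 | 3.33 | 23.1% |
| 20 | 4 | 96 | 60 | 4.17 | 6.67 | 37.5% |

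**Sensitivity to converter follow-up.** Take N = 60, x = 3, Fn = 3, c = 4. With converters followed to month 24, T = 171 + 72 = 243 and R = 171 + 12 = 183. The rate is 1.23 against 1.64, about 25% low. With converters followed only to month 6, T = 171 + 18 = 189 and the rate is 1.59 against 1.64, about 3% low.

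**Zero converters.** If the true proportion were 2% (assumed), the chance of a zero count is 0.98^60 = 0.30 or 0.98^20 = 0.67. Zero still carries information. With 6 months per subject, the exact upper limit of the 80% interval for the rate is −ln(0.1)/T × 100, which is 2.303/360 × 100 = 0.64 per 100 person-months for N = 60, and 2.303/120 × 100 = 1.92 for N = 20. For the proportion, 0/60 gives 0 to 3.8% and 0/20 gives 0 to 10.9%.

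**Reversed wording.** Suppose 2 of 20 are MRD-negative and all others count as not negative. The endpoint is 10% (80% interval 2.7% to 24.5%). The summary sentences, read literally, ask for 18/20 = 90% (75.5% to 97.3%).

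**The case against.** A reader might infer that the plan as a whole misstates the endpoint and reports it selectively. The documents do not support that. SAP 9.5.2.2 opens by requiring the MRD-negative proportion with an exact interval. That measure has the right direction, uses no person-time and matches the endpoint. The zero condition follows the rate formula, so its natural reading covers the rate alone; the proportion would still appear as 0% with its interval. The Clopper-Pearson code in Appendix A, although written for the response rate, handles zero events. What is lost at zero is only a rate equal to zero. The pronoun in that sentence is slightly ambiguous, which calls for clarification and does not show selective reporting.

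A single figure such as 25% also overstates what is known. It needs converters followed to month 24 and everyone else for 3 months. Protocol 3.5.1 anticipates about 6 months of treatment and 7.5 months on study, and at 6 months of follow-up the same example is only 3% low. Longer follow-up is possible, so only a range can be given. Moreover, counting time after conversion is the literal reading of an undefined term and not an explicit rule.

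Nor is it a fault in itself that most of the denominator comes from subjects never tested. Counting all treated subjects parallels the objective response rule in SAP section 5, under which those who do not meet the criteria are non-responders.

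Finally, the study is non-randomised and descriptive, and no dose decision or stopping rule uses this rate. All of this stands, and it limits the point. It does not supply the missing clock stop, restore the rate at zero, or remove the contradiction in wording. The Protocol's statistical section has no sentence of its own that corrects the direction.

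**Conclusion.** The concern holds for one of the two planned measures and for two summary sentences. The written rate falls as converters are followed longer. Under the assumed inputs it is about 1% to 17% low with equal follow-up (1 to 4 converters, 6 or 12 months) and about 9% to 38% low when converters are followed for 12 months and others for 3. The upper ends come from 20 subjects. With 60, the corresponding upper ends are about 6% and 17%, and the effect is negligible with few converters and equal follow-up. These sizes rest on assumed counts, conversion times and follow-up, and on reading the denominator literally.

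The omission at zero and the reversed phrase need no assumption: both are on the page. The MRD-negative proportion is sound. The rate is also absent from Protocol 10.4.4.1, although SAP section 10 declares no departures from the protocol's analyses.

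**What to change.** 1. In SAP 9.5.2.2, delete the person-month rate. If it is kept, define person-time as running from the first dose to conversion or, without conversion, to the last assessment, and report the rate when the count is zero.
2. State that the MRD-negative proportion over the Safety Analysis Set, with its exact 80% interval and including a zero count, is the analysis of the conversion endpoint. Say that subjects without an MRD test count as not MRD-negative.
3. In Protocol 10.4.4.1 and SAP 9.5.2, reword the summary sentence so that it asks for the proportion of subjects with MRD negativity.
4. Optional: add the proportion among subjects with a complete response and an MRD test, labelled as a subset.

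The cost is wording in the SAP and one phrase in the protocol. No new data, visits or subjects are needed.

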9.5.2.3 Progression Free Subject Rate

The proportion of subjects who are progression free (IMWG-URC) at 6 months with corresponding exact 80% CI will be calculated using the Clopper-Pearson method.

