3.5.2 End of Study

The end of study occurs when a subject discontinues treatment with AMG 224 and completes the EOS visit. The date the final safety assessment or procedure is performed is considered the end of study. The safety follow-up or EOS visit will occur 30 to 37 days after the last administration of AMG 224.

Primary Completion is defined as the time when the last subject is assessed or receives an intervention for the purposes of final collection of data for the primary analysis. The

Approved

primary analysis will occur when target enrollment is complete and each subject either completes 6 months on study or withdraws from the study. Subjects who are still active at the time of the primary analysis may continue on study until disease progression, study withdrawal, death, or investigational product intolerance is observed

End of Trial is defined as the time when the last subject is assessed or receives an intervention for evaluation in the study. Once achieved, the final analysis will occur.

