7.2.24 End of Study Visit

The EOS visit must be performed 30 to 37 days after the last dose of AMG 224. All efforts should be made to conduct this visit. If it is not possible to conduct the EOS visit, documentation of efforts to complete the visit should be provided in the source documents and noted as not done in the eCRFs.

Clinical evaluation to include the following:

- Physical examination with neurological assessment and ECOG performance status
- Vital signs (blood pressure, respiratory rate, heart rate, temperature)
- Peripheral neuropathy assessment
- 12-lead ECG
 - collected after subject has rested for 5 minutes.
 - record QRS, QT, QTc, RR and PR intervals.
- Safety Laboratory Assessments (locally tested)
 - Chemistry
 - Hematology
 - Coagulation
 - Urinalysis
- Blood collection
 - Biomarker
 - Anti-AMG 224 antibody
- Serum protein electrophoresis (SPEP) and 24-hour urine protein electrophoresis (UPEP)
- Serum free light chain (SFLC)

Approved

- Adverse event assessment is performed throughout the study at every visit
 - Serious adverse events are collected from the time the subject signs the ICF.
 - Adverse events are collected from the time the subject is dosed on day 1.
- Documentation of concomitant medications

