8. WITHDRAWAL FROM TREATMENT, PROCEDURES, AND STUDY

8.1 Subjects' Decision to Withdraw

Subjects have the right to withdraw from the study at any time and for any reason without prejudice to their future medical care by the physician or at the institution.

Subjects (or a legally acceptable representative) can decline to continue receiving investigational product and/or other protocol required therapies or procedures at any

time during the study but continue participation in the study. If this occurs, the investigator is to discuss with the subject the appropriate processes for discontinuation from investigational product or other protocol required therapies and must discuss with the subject the options for continuation of the Schedule of Assessments ([Table 5.](#)) and collection of data, including endpoints and adverse events. The Investigator must document the change to the Schedule of Assessments ([Table 5.](#)) and the level of follow-up that is agreed to by the subject (eg, in person, by telephone/mail, through family/friends, in correspondence/communication with other physicians, from review of the medical records).

Withdrawal of consent for a study means that the subject does not wish to receive further protocol-required therapies or procedures, and the subject does not wish to or is unable to continue further study participation. Subject data up to withdrawal of consent will be included in the analysis of the study, and where permitted, publicly available data can be included after withdrawal of consent. The investigator is to discuss with the subject appropriate procedures for withdrawal from the study.

8.2 Investigator or Sponsor Decision to Withdraw or Terminate Subjects' Participation Prior to Study Completion

The investigator and/or Amgen can decide to withdraw subjects from investigational product and/or other protocol required therapies, protocol procedures, or the study as a whole at any time prior to study completion.

Subjects may be eligible for continued treatment with Amgen investigational product(s) and/or other protocol required therapies by a separate protocol or as provided for by the local country's regulatory mechanism, based on parameters consistent with [Section 12.1.](#)

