4.2 Subgroups

Biomarker data may be incorporated in additional exploratory subgroup or multivariate analyses. The analyses of biomarkers may be performed after collection of all samples

during the conduct of the study and therefore may be reported after the primary analysis of efficacy endpoints.

5. Definitions

Age at Enrollment

Subject age at enrollment will be determined using the age in years reported in the clinical database.

AUC_{0-3 week} = AUC_{0-504 hrs}

It is defined as the area under the concentration-time curve from time 0 to 504 hours.

Baseline

Unless otherwise specified the baseline value for parameters/assessments scheduled to be performed on the same day as the first administration of AMG 224 (Q3W), is the last value measured before the first administration of AMG 224 on that day. For parameters/assessments not scheduled to be performed (or scheduled but not performed) on the same day as the first administration of AMG 224, the baseline value is the value from the screening period measured closest to the day of first administration of AMG 224. In the event that multiple assessments are done on the same day as the first administration of AMG 224 and there is no time associated with the assessments, the value associated with the last clinically planned event before the first administration of AMG 224 will be used as the baseline value.

For baseline ECG, three triplicate ECGs to be collected ≥ 30 minutes apart, with each ECG in triplicate approximately 30 seconds apart (3 set collected predose on day 1 with total of 9 ECGs) planned to be taken predose. Mean value will be calculated and used in the analysis. The mean of the values within a triplicate should be calculated before taking the mean of the triplicate averages. Where an ECG is missing within a triplicate, all available data will be averaged for that time point.

Best Overall Response

Best overall response for a subject is the best observed post baseline disease response per the International Myeloma Working Group Uniform Response Criteria for Multiple Myeloma (IMWG-URC).

Best Overall Response/Progression CRF will be employed to determine the response.

Every effort should be made to document the objective progression even after discontinuation of treatment.

Body Mass Index (BMI)

Body Mass Index should be calculated using the following formula

$$\text{BMI (kg/m}^2\text{)} = \text{weight (kg)} / [\text{height (cm)} / 100]^2$$

Change From Baseline

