9.5.2.4 Time to progression

Time to progression (IMWG-URC) will be analyzed using the Kaplan-Meier method. Kaplan-Meier survival curves and median time to progression along with 80% CI will be presented.

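### The 6-month progression-free rate is a simple proportion with no rule for subjects who leave early or die without progression; the Kaplan-Meier estimate already planned would handle both

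*SAP*

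**What the plan says.** **The 6-month figure.** SAP 9.5.2.3: "The proportion of subjects who are progression free (IMWG-URC) at 6 months with corresponding exact 80% CI will be calculated using the Clopper-Pearson method". Protocol 10.4.4.1 likewise plans the proportion "progression-free at 6 months with corresponding exact 80% CI will be calculated using the Clopper-Pearson method". Neither gives a denominator or a rule for unknown status. By default SAP 9.1 makes the denominator the Safety Analysis Set. SAP 8.3 covers only incomplete dates and values below quantification.

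**Kaplan-Meier is already planned.** SAP 9.5.2 and protocol 10.4.4.1 plan curves for time to progression and duration of response "with estimates for rates and 80% CI at selected weeks"; the weeks are not named. SAP 9.5.2.4 adds: "Kaplan-Meier survival curves and median time to progression along with 80% CI will be presented". SAP section 5 counts progression or death as the event for time to progression and censors other subjects at their last evaluable assessment.

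**Follow-up.** Protocol 3.5.2: "The end of study occurs when a subject discontinues treatment with AMG 224 and completes the EOS visit". Protocol 7.2.24: "The EOS visit must be performed 30 to 37 days after the last dose of AMG 224". Two passages soften this. SAP section 5, under Best Overall Response, says: "Every effort should be made to document the objective progression even after discontinuation of treatment". Protocol 8.1 lets a subject decline treatment at any "time during the study but continue participation in the study". Neither sets a visit schedule after the end-of-study visit.

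**The concern.** A binomial proportion needs a yes or no for every subject. Subjects who stop for toxicity, a long dosing delay or their own choice can leave before 6 months without progression, and their status is then unknown. The response rate has an explicit rule (SAP section 5 counts subjects who do not meet the response criteria as non-responders), but the 6-month rate has none. The likeliest reading, with the Safety Analysis Set as denominator and only subjects known to be progression-free in the numerator, scores partial follow-up as failure.

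Deaths are also unclassified. SAP 9.5.2.3 refers to the IMWG criteria, and the progression criteria in protocol Appendix D do not list death. The same death is an event in the curve of SAP 9.5.2.4. A reader could therefore see two 6-month figures that differ only through unstated coding, and could take a curve that counts deaths as time to progression alone. If the coding is chosen after the data are seen, in an open-label study, it could move the reported rate by several points.

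**Working it through.** **1. The plan's own interval.** Two-sided 80% Clopper-Pearson for 4/20 is 9.0% to 36.1%; SAP 3.2 states 9% to 36%. The arithmetic is sound, so the question is the estimator.

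**2. Can follow-up end before 6 months?** With on-schedule dosing every 3 weeks, dose k falls on day 1 + 21(k − 1). Six months is about day 183.

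| Last dose | Day | End-of-study visit (+30 to +37) |
|---|---|---|
| 7 | 127 | 157 to 164 |
| 8 | 148 | 178 to 185 |
| 9 | 169 | 199 to 206 |

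A last dose at dose 7 or earlier ends scheduled follow-up before 6 months.

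**3. Hypothetical example, n = 20.** Four progress before month 3, four leave at month 3 without progression, four progress after month 3, and eight are progression-free at 6 months.

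- Leavers as failures: 8/20 = 40% (80% CI 25 to 57%)
- Leavers dropped: 8/16 = 50% (32 to 68%)
- Leavers as progression-free: 12/20 = 60% (43 to 75%)
- Kaplan-Meier: (16/20) × (8/12) = 53% (log-log 80% CI 36 to 68%)

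**4. Long-run values.** The documents give no 6-month rate or stopping rate, so these are assumptions: true rate 40%; 10%, 30% or 50% stopping by 6 months; 1.1 months of follow-up after stopping; correlation between stopping and progression times 0 or 0.5; progression seen at its exact time; 1,000,000 simulated subjects per case. The column for unknowns as progression-free is the failure column plus the unknown share.

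| Correlation, stopping | Unknown | As failure | Dropped | As progression-free | Kaplan-Meier |
|---|---|---|---|---|---|
| 0, 10% | 0.049 | 0.367 | 0.386 | 0.416 | 0.400 |
| 0, 30% | 0.153 | 0.299 | 0.353 | 0.452 | 0.400 |
| 0, 50% | 0.266 | 0.227 | 0.310 | 0.493 | 0.401 |
| 0.5, 10% | 0.019 | 0.393 | 0.400 | 0.412 | 0.405 |
| 0.5, 30% | 0.088 | 0.358 | 0.393 | 0.446 | 0.419 |
| 0.5, 50% | 0.189 | 0.305 | 0.376 | 0.494 | 0.438 |

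**5. Progression seen only at 21-day visits and the end-of-study visit.** Detection lags, so even complete follow-up reads 43%. At 10% / 30% / 50% stopping:

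- Failure coding: 0.394 / 0.321 / 0.244 (correlation 0) and 0.421 / 0.382 / 0.323 (correlation 0.5)
- Kaplan-Meier: 0.427 / 0.423 / 0.418 and 0.434 / 0.443 / 0.456

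**6. Precision at n = 20, exact progression times.** Root mean square error, Kaplan-Meier v failure coding:

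- Correlation 0: 0.112 v 0.113, 0.120 v 0.144, 0.128 v 0.195
- Correlation 0.5: 0.111 v 0.110, 0.116 v 0.116, 0.128 v 0.141

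The nominal 80% log-log Kaplan-Meier interval covered 79 to 82%.

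**7. Deaths.** Assume a share f of events are deaths without progression, with constant hazards and a 6-month rate of 40% for progression or death. Censoring deaths gives 0.40^(1 − f): 0.438 at f = 0.1 and 0.480 at f = 0.2. Counting such deaths as progression-free in the proportion gives 0.40 + 0.60f: 0.46 and 0.52.

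**The case against.** **Partial follow-up is already used.** The plan has Kaplan-Meier curves, censoring rules and rates at selected weeks. This stands in part: the remedy names a time point, chooses the headline figure and states a rule. It does not add a new method.

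**A reader might infer that the proportion always understates the rate.** The documents do not support that. No coding is stated; counting unknowns as failures biases the rate low, and counting them as progression-free biases it high.

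**A reader might infer that Kaplan-Meier is better throughout.** It is not. When progression is seen only at visits, the answer depends on the benchmark. Against the true 40%, failure coding had the smaller root mean square error at n = 20 in four of six cases, including all three with correlated stopping (0.112 v 0.116, 0.111 v 0.123, 0.128 v 0.133 for Kaplan-Meier). Kaplan-Meier was better at 30% and 50% independent stopping (0.123 v 0.132 and 0.128 v 0.183). Against the 43% seen with complete follow-up, Kaplan-Meier was better in five of six and about equal in the other. With exact progression times, dropping unknowns is nearer 40% than Kaplan-Meier in the three correlated cases. Exits for intolerability or clinical deterioration may well track prognosis, so the largest gaps rest on the less plausible assumption.

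**A reader might infer that the SAP changed the time-to-progression endpoint without declaring it.** The protocol lists the endpoint but never defines it, and the SAP states its definition openly. Supplying a definition does not contradict SAP section 10. What stands is a labelling problem.

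**Conclusion.** The point holds as a minor one: a cheap improvement. The 6-month rate is planned with an estimator that cannot use partial follow-up, and no rule covers unknown status or deaths without progression. The design allows both, but the documents do not show how many there would be.

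Under the assumptions above with exact progression times, failure coding reads about 1 to 17 points below 40%, and counting unknowns as progression-free reads about 1 to 9 points above. Kaplan-Meier is unbiased when stopping is unrelated to prognosis. If stopping tracks prognosis it runs about 0.5 to 4 points high. With visit-based detection in those correlated cases it is about 3 to 6 points above 40%, or up to about 3 points above the 43% of complete follow-up. At n = 20 the gain is negligible when few stop early.

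The figure is a descriptive secondary summary and not a listed endpoint. It does not touch the MTD, the stopping rules or the sample size.

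**What to change.** (a) In SAP 9.5.2 and 9.5.2.3 and protocol 10.4.4.1, name 6 months among the Kaplan-Meier time points. Report the progression-or-death estimate, with an 80% CI (Greenwood variance, log-log scale), as the 6-month progression-free rate.

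(b) Keep the Clopper-Pearson proportion as a conservative companion. State that unknown status and death without IMWG progression both count as not progression-free, and report the number unknown.

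(c) In SAP section 5 and 9.5.2.4, label the curve that counts deaths as progression-free survival, so that the listed time-to-progression endpoint is not misread. A separate time-to-progression curve with deaths censored is optional.

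If the protocol text is left unchanged, record the new headline estimate in SAP section 10.

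Cost: wording, and one more curve if the option in (c) is taken; no new data. The downside is that Kaplan-Meier assumes non-informative censoring, with the upward error given above, and its interval is approximate at about 20 subjects. The companion figure and the count of unknowns let a reader judge how much that matters.
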